PROTOCOL

Selective Coronary Revascularization in Carotid Artery Disease patients after carotid revascularization (SCORECAD trial)

Working draft protocol version number: *Latvia RCT/CAD/25062024*

Universal Trial Number: *ClinicalTrials.gov TBA*

In the following, Institute of Science, Pauls Stradiņš Clinical University Hospital and its affiliates will be stated as “Stradiņš University Hospital”.

This confidential document is the property of Stradiņš university hospital. No unpublished information contained herein may be disclosed without prior written approval from Stradiņš university hospital. Access to this document must be restricted to relevant parties.

DOCUMENT HISTORY		
Document version	Date	Applicable in country(-ies) and/or site(s)
1.0	25 June 2024	All

Study Objective To determine whether the diagnosis of ischemia-producing coronary stenosis together with selective coronary revascularization in carotid artery stenosis (CAS) patients following carotid revascularization can reduce adverse cardiac events and improve survival compared to carotid patients receiving standard cardiac evaluation and treatment.

Study Design Multicenter, prospective randomized clinical trial of patients with symptomatic or asymptomatic CAS patients, and no known CAD who had undergone a carotid revascularization procedure (endarterectomy or stenting). Eligible patients will be randomly assigned to receive (a) current guideline-directed care with evidence-based best medical therapy (BMT) and risk factor control or (b) in addition to BMT and

risk factor control, non-invasive cardiac evaluation using coronary CTA and FFRct to identify ischemia-producing coronary lesions together with selective ischemia-targeted coronary revascularization. The primary outcome measure will be MACE (cardiac death, myocardial infarction, urgent (unplanned) coronary revascularisation) during 2 years follow up with secondary endpoints of myocardial infarction, cardiac death, urgent coronary revascularisation, cardiovascular death and all-cause death.

Principal Investigator:

[name], PhD and principal Co-investigator [name] [name]

Pauls Stradiņš Clinical University hospital

[name]

[name]

[contact]; [contact]

[name]; [name]

Co-investigators & Steering committee: [name] MD; [name] [name]; [name] [name]; [name] [name]; [name] [name]; [name] [name] and others TBA.

Study Sites:

Pauls Stradiņš Clinical University Hospital plus up to 10 additional sites

CRO:

Institute of Science, Pauls Stradiņš Clinical University Hospital

Study Sponsor:

Pauls Stradiņš Clinical University Hospital with a grant from the TBA.

I. BACKGROUND

Coronary artery disease (CAD) is the primary cause of morbidity and mortality in patients with carotid artery disease. Patients with asymptomatic carotid stenosis have a four-fold higher risk of myocardial infarction (MI) than stroke¹ and the presence of carotid stenosis is an independent predictor of cardiac death.^{2,3} Patients undergoing carotid endarterectomy (CEA) have a higher risk of myocardial infarction (MI) than stroke and those with post-op MI have a 5 year survival of only 56%.⁴ Despite this high cardiac risk and the knowledge that 60% of carotid endarterectomy patients have coronary angiographic evidence of significant CAD (>70% stenosis),⁵ systematic pre-operative cardiac testing is not recommended for vascular surgery patients since randomized trials have shown no long-term survival benefit from pre-operative coronary revascularization.⁶ Guidelines specifically note that cardiac testing should not be performed in patients with no coronary symptoms⁷ and thus most patients undergo major vascular surgery without pre-operative cardiac testing and mortality of patients with post-op MI remains high despite evidence-based medical therapy.⁸

Myocardial ischemia is common in patients with CAD, is often asymptomatic (silent), and is a marker for adverse cardiac events and reduced survival.⁹ Pre-operative non-invasive testing of patients undergoing carotid or peripheral vascular surgery showed that 25-40% of patients had silent ischemia and that silent ischemia was a predictor of adverse outcomes.¹⁰⁻¹² While cardiac stress testing provides valuable information on myocardial perfusion, it does not provide actionable information regarding coronary artery lesions which may be producing ischemia and which may benefit from revascularization. The ischemic potential of a coronary stenosis can be determined at the time of coronary angiography by measurement of fractional flow reserve (FFR). Randomized trials of patients with stable CAD and lesion-specific coronary ischemia as demonstrated by $FFR \leq 0.80$ in at least one large coronary artery have shown that FFR-guided coronary revascularization results in a significant reduction in death/MI at 5 years compared to medical therapy.^{13,14}

A newly introduced non-invasive diagnostic modality, coronary CT-derived fractional flow reserve (FFR_{CT}) provides a unified anatomic and functional assessment of coronary artery disease which can reliably identify ischemia-producing coronary lesions.¹⁵ FFR_{CT} analysis is based on anatomic information provided by coronary CTA with computational analysis of coronary blood flow to provide fractional flow values throughout the coronary tree. FFR_{CT} accurately reflects invasively measured FFR¹⁶ and can help guide patient management decisions.^{17,18} The clinical usefulness of FFR_{CT} is well documented¹⁹ and FFR_{CT} analysis is now being used in the US, Europe, Canada and Japan to evaluate stable patients with symptoms of CAD. The usefulness of FFR_{CT} in evaluation of patients without cardiac symptoms is unknown.

In a prospective, single-center, observational study of patients with no known CAD undergoing CEA, a strategy of pre-operative cardiac evaluation using coronary CTA and FFRCT, along with ischemia-guided coronary revascularization following CEA, resulted in a more than 50% reduction in all-cause

death, cardiac death, myocardial infarction, and MACE, with improved 5-year survival compared to patients receiving standard cardiac evaluation and care (84% vs 64%, $p < .001$)²⁰⁻²¹.

The purpose of this study is to determine the prevalence of silent coronary ischemia in patients undergoing carotid revascularization (endarterectomy or stenting) using coronary CTA and FFR_{CT} and to evaluate the potential usefulness of FFR_{CT} in selecting patients for coronary revascularization to reduce cardiac events and improve survival.

II. OBJECTIVE

The primary objective of this study is to determine whether among symptomatic and asymptomatic CAS patients with no known CAD who had undergone carotid artery revascularization (endarterectomy or stenting) a strategy of best medical therapy (BMT) plus selective coronary revascularization based on FFR_{CT} assessment of lesion-specific coronary ischemia can reduce adverse cardiac events and improve survival compared to BMT alone. Lesion-specific coronary ischemia is defined as FFR_{CT} ≤ 0.80 distal to stenosis in a major (≥ 2 mm) coronary artery with severe ischemia defined as FFR_{CT} ≤ 0.75 .

III. STUDY ENDPOINTS

The primary endpoint of the study is a composite of cardiac death, myocardial infarction (MI) or urgent (unplanned) coronary revascularisation (MACE) during 2 years follow up. Secondary endpoints include cardiac death, MI, urgent coronary revascularisation, cardiovascular (CV) death, all-cause death during follow up.

IV. STUDY DESIGN

This study targets a population of patients with symptomatic or asymptomatic carotid artery stenosis (CAS) (symptomatic to asymptomatic in 1:1 ratio) and no prior cardiac history, no myocardial infarction, no coronary angiography or coronary CTA, and no coronary revascularization (PCI or CABG) who have undergone successful carotid artery revascularisation with planned post-operative best medical therapy. Within 14 days following carotid revascularisation, patients will be randomly assigned to BMT alone or BMT plus coronary CT angiography (which must be completed within 14 days of randomization) and FFR_{CT} analysis to determine the functional significance of coronary lesions identified on the CT scan. Results of the CT scan and FFR_{CT} analysis in patients randomized to the CT-FFR_{CT} group, will be provided to treating physicians to help guide patient management with Vascular Heart Team consideration for coronary angiography and revascularization as appropriate for each patient. Coronary revascularisation (PCI or CABG), if indicated, is strongly recommended within 3 months from the randomisation. Clinical follow up (based on date of randomization) is planned 6 months, one and 2 years. Additional long-term follow up out to 5-years is planned for participating centers. An independent academic clinical events committee will adjudicate all endpoints in a blinded manner. The definition of outcome events will be in

accordance with Academic Research Consortium-2 consensus document²². Sample size power calculations assumed a hazard ratio of 0.5 with estimated sample size up to 300 patients (up to 150 in each group), 90% power, alpha .05. The patient sample size may be reduced if statistical significance been achieved.

V. INCLUSION AND EXCLUSION CRITERIA

Inclusion Criteria

1. Inform consent obtained before any study-related activities
2. Age above or equal to 50 years with symptomatic or asymptomatic critical carotid stenosis (symptomatic patients with at least Rankin III.) which has been successfully revascularized by carotid endarterectomy or stenting within the past 14 days
3. Willing and able to undergo coronary CTA scan within 14 days of randomization and agrees to submission of CTA data set for HeartFlow FFRct analysis with results made available to treating physician

Exclusion Criteria

1. Known CAD, history of MI, prior coronary revascularization (PCI or CABG)
2. Patient underwent coronary angiography or coronary CTA before the randomization
3. Known history of 2nd or 3rd degree heart block; sick sinus syndrome; long QT syndrome
4. History of severe asthma, severe or bronchodilator-dependent COPD
5. Severe congestive heart failure (NYHA III or IV)
6. Severe arrhythmia, prior pacemaker or internal defibrillator lead implantation
7. Impaired chronic renal function (EPI-GFR \leq 30ml/min)
8. Subjects with known anaphylactic allergy to iodinated contrast
9. Pregnancy or unknown pregnancy status in subject of childbearing potential
10. Evidence of ongoing or active clinical instability, including acute chest pain (sudden onset), cardiogenic shock, unstable blood pressure with systolic blood pressure <90 mmHg, or acute pulmonary edema
11. Any active, serious, life-threatening disease with a life expectancy of less than 2 years
12. Any active infection
13. Inability to comply with study procedures
14. Contraindication for guideline-guided longterm antiplatelet/anticoagulation regime after PCI/CABG
15. Large neurologic deficit (Rankin scale $>III$)

16. Participation in any interventional clinical study within 30 days prior to screening

VI. Rules for subject withdrawal and terminating the study

In accordance with the Declaration of Helsinki, as amended, each subject is free to withdraw from the study at any time. Investigator(s) also have the right to withdraw subjects from the study in the event of illness, adverse events (AEs), serious adverse events (SAEs), other reasons concerning the health or well being of the subject, or in the case of lack of cooperation. The reason for withdrawal must be noted in the Case Report Forms (CRFs). If the reason for withdrawal is a clinical AE or SAE, follow up of the subject will continue until the outcome is evident. The specific event or test result(s) must be recorded in the CRFs.

There are no formal termination criteria for this study. The sponsor reserves the right to terminate the study at any time. Investigators have the responsibility to comply with International Conference on Harmonization E6-Good Clinical Practice (ICH E6 - GCP) guidance. The sponsor, the IRB, or the health authorities may terminate a center for the following (but not limited to) reasons:

- 1) Failure of the investigator to comply with pertinent E6-GCP guidelines and regulations
- 2) Serious protocol violations
- 3) Submission of knowingly false information from the research facility.

VII. Ethical Considerations

The potential benefits to all subjects participating in this study is that they may receive closer monitoring and follow up with better compliance to guideline-recommended BMT and risk factor control. Patients randomized to the coronary CTA-FFRct arm of the study will have additional benefit of specific cardiac diagnosis and treatment. Prior studies have demonstrated that PAD patients often have unrecognized coronary artery disease and that they have a high risk of cardiovascular complications including MI and cardiovascular death. Current guideline-directed pre-procedure cardiac evaluation of PAD patients without cardiac symptoms does not include cardiac imaging or stress testing. Half of enrolled subjects within the study will undergo coronary artery CT scanning which is highly sensitive for detecting CAD. Subsequent FFRct analysis will identify those with hemodynamically significant coronary stenosis. The incremental potential risks to subjects participating in the study are solely and directly related to the performance of the additional cardiac diagnostic testing in half of the patients.

VIII.A. Risks of Coronary CTA

Coronary CTAs expose subjects to small amounts of ionizing radiation. Since the introduction of 64-detector row CTA scanners in 2005, numerous radiation dose reduction methods have been developed which now permit CTA performance with low overall radiation dose. Minimization of radiation dose while preserving image quality is a goal of the study; optimization of radiation dose may be achieved by

a by a combination of 7 additive dose reduction strategies: ECG dose modulation; Weight-based tube voltage; Prospective ECG triggering; Minimization of "padding"; Minimization of Z-axis coverage; Limiting of the field of view (FOV); Automatic exposure control. Coronary CTA performance necessitates the use of iodinated contrast. Minor reactions to x-ray contrast material can occur, including itches or hives with an incidence of approximately 1 in 200 subjects. More severe reactions that are very infrequent include hypotension, laryngospasm and bronchospasm. The incidence of these reactions is estimated at about 1 in 5,000 and is treated with intravenous epinephrine. Extravasation of x-ray contrast material outside the vein during injection may occur and result in a painful soft tissue swelling and bruising. Subjects will be monitored for extravasation during injection and the amount of contrast material injected into the tissues is usually quite small without significant clinical consequences.

VIII.B. Risks of FFR_{CT} analysis

In subjects with Coronary CTA, FFR_{CT} analysis will be performed using the clinically acquired Coronary CTA data set. The FFR_{CT} analysis in these subjects does not require additional imaging, medication or radiation exposure. There is no additional risk to the subject.

IX. STUDY PROTOCOL REQUIREMENTS

1. After providing informed consent, each subject will undergo the following assessments as indicated on CRF:
 - a. Collection of demographic information, including height, weight, presenting symptoms and neurologic status.
 - b. A summary of index carotid revascularization procedure
 - c. A summary of the subject's relevant medical and surgical history (Diabetes mellitus, Dyslipidemia, Arterial hypertension, Smoking)
 - d. Recording of concurrent and concomitant medications
2. Coronary CTA (cCTA) Procedure
 - . 1) Perform cCTA with strict adherence to SCCT guidelines including, but not limited to:
 - a. Heart rate control: administration of β -blockers, if needed, to achieve a heart rate of <60 bpm
 - b. CT image acquisition after administration of sublingual nitrate spray or after administration of sublingual nitrate tablet (3-5 minutes)
 - c. using breath-holding and other techniques to minimize motion artifact
 - d. contrast protocols: bi-phasic injection protocol
 - e. kV/mA settings per ALARA principles. Patients who weigh more than 70kg should be scanned at 120kV.
 - 2) The additional thorax CT findings (pulmonary oncology, etc.) might be collected at selected sites.

3. Post-procedure follow up data from clinical visits and/or phone calls 3 months, one and 2 years (annually up to 5 years for patients entering prolonged study at participating sites).
4. Open label randomization will be done after patient screening at approximate rate 1:1 symptomatic to asymptomatic CAS.

X. Case Report Forms

Electronic or paper case report forms will be used.

XI. Institutional Review

Before starting this study, the protocol will be submitted to the regulatory bodies/local health authorities (in accordance with local regulations) and the study will not start before the EC/IRB gives written approval or a favorable opinion in accordance with ICH E6-GCP and all applicable regulatory bodies/local health authorities give approval or a favorable opinion as required.

XII. Informed consent

Written and oral information about the study in a language understandable by the subject will be given to all subjects by the investigator and/or designee. The subject's willingness to participate in the study will be documented in writing in a consent form, which will be signed by the subject with the date of that signature indicated. The investigators will keep the original consent forms and copies will be given to the subjects. The informed consent will also be signed and dated by the person who conducted the informed consent discussion.

XIII Confidentiality regarding study subjects

The investigator(s) must assure that the privacy of the subjects, including their personal identity and all other personal medical information, will be maintained at all times. In documents or image material submitted to the sponsor, subjects will not be identified by their names, but by an identification code. Personal medical information may be scrutinized for the purpose of verifying data recorded in the CRF. This may be done by properly authorized persons, the quality assurance unit, or regulatory authorities. Personal medical information will always be treated as confidential.

XIV Financial Disclosure

The investigator(s) (or investigating institution) will provide the sponsor with accurate financial disclosure regarding real or potential financial conflicts of interest.

XV Insurance

As there is no any invasive investigation product been tested, the local site clinical liability insurance will be in power to cover malpractice.

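### Is the stated 90% power wrong because the protocol gives no control event rate for two-year MACE?

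*Protocol*

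**What the plan says.** Section III defines the primary endpoint as the composite of death from a cardiac cause, infarction or "urgent (unplanned) coronary revascularisation (MACE) during 2 years follow up". Section IV sizes the trial on a "hazard ratio of 0.5 with estimated sample size up to 300 patients (up to 150 in each group), 90% power, alpha .05". It then adds: "The patient sample size may be reduced if statistical significance been achieved".

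That is all the protocol says about size. It gives no control-arm MACE rate, required number of events, one- or two-sided alpha, or allowance for patients lost to follow-up.

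**The concern.** A log-rank or Cox comparison draws its power from events. Once the hazard ratio, alpha, number of patients and length of follow-up are fixed, a claim of 90% implies a particular control event rate. Here that rate is high, more than one control patient in three within two years on a two-sided test, in people enrolled because they have no known coronary disease. None of the percentages in Section I is a two-year MACE rate.

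If the true rate were well below the implied one, the trial would have a much larger chance than 10% of missing a real halving of MACE, and a null result could be read as stronger evidence against the strategy than it is.

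**Working it through.** **Inputs from the protocol.** Hazard ratio 0.5, 150 per arm, power 90%, alpha 0.05 (Section IV); two years of follow-up for the primary endpoint (Section III).

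**Assumptions added here.** 1:1 allocation, proportional and constant hazards, no competing-risk adjustment, one analysis at full enrolment. Both sidedness readings are shown.

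**Can the 90% be reproduced?** Not from the stated inputs alone, because no event rate is given. The check therefore solves for the rate that would make it true.

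*Step 1, events needed.*
- Schoenfeld, two-sided: 4 × (1.960 + 1.2816)² / (ln 0.5)² = 87.5
- Schoenfeld, one-sided: 4 × (1.645 + 1.2816)² / (ln 0.5)² = 71.3
- Freedman: 95 two-sided, 78 one-sided

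*Step 2, control rate p that yields those events.* Under proportional hazards the expected events are 150 × [p + 1 − (1 − p)^0.5].
- Schoenfeld: p = 37.4% two-sided (CTA arm 20.9%), 30.7% one-sided
- Freedman: p = 40.5% two-sided, 33.5% one-sided
- Schoenfeld with 10% lost and giving no events (135 per arm): p = 41.4% and 34.0%

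*Step 3, power at other control rates.* Power = Φ(√d / 2 × ln 2 − z), where d is the number of events.

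| Control two-year MACE | Events, no loss | Two-sided / one-sided power, no loss | Two-sided / one-sided power, 10% loss |
|---|---|---|---|
| 20% | 45.8 | 65% / 76% | 60% / 72% |
| 25% | 57.6 | 75% / 84% | 70% / 80% |
| 30% | 69.5 | 82% / 89% | 78% / 86% |
| 37.4% | about 87 | 90% / 94% | 87% / 92% |

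A simulated log-rank test (150 per arm, 10,000 runs, no loss) gives two-sided power of 63%, 72%, 81% and 90% in the same rows, so the formula is at most about 3 points optimistic. The 20%, 25% and 30% rows are illustrative and do not come from the protocol.

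*Step 4, does any protocol figure confirm or refute a rate near 37%?* All of these are in Section I.
- "60% of carotid endarterectomy patients have coronary angiographic evidence of significant CAD": a prevalence of disease, not an event rate.
- "25-40% of patients had silent ischemia and that silent ischemia was a predictor of adverse outcomes": also a prevalence.
- "those with post-op MI have a 5 year survival of only 56"%: survival after a postoperative infarction, over five years.
- The observational study "resulted in a more than 50% reduction in all-cause" death and, in the same list, MACE. This is a relative effect. It can motivate a hazard ratio of 0.5 but fixes no baseline.
- "improved 5-year survival compared to patients receiving standard cardiac evaluation and care (84% vs 64"%: death from any cause over five years. At constant hazard the control figure becomes 1 − 0.64^0.4 = 16% dead at two years. MACE leaves out non-cardiac death and adds non-fatal infarction and urgent revascularisation, so its rate may be higher or lower than 16%. The figure is not a bound.

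Nothing in the list supports 37%, and nothing rules it out.

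**The case for a change.** The best case for acting is that the protocol did not leave the power calculation for later. It states the result, and that result is its only justification for 300 patients. Section V excludes known coronary disease, previous infarction and previous revascularisation, so a two-year rate above 30% calls for a source. There is also a suggestive coincidence: 36% control mortality at five years (100% − 64%), used as if it were the control event rate, gives 150 × (0.36 + 0.20) = 84 events and 89% two-sided power, close to the stated 90%. A five-year mortality figure may have been used for a two-year MACE rate.

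Part of this stands. A reader cannot verify the 90%, and a sentence naming the assumed rate and its source would have been better reporting. The rest does not amount to an error. The coincidence is conjecture. The population argument shows that a source would be welcome, not that the rate is false. The observational comparison in Section I was in carotid endarterectomy patients with no known coronary disease and reported MACE, so its control arm is a natural source for the rate, although the protocol does not quote it.

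The provision for reducing enrolment does not strengthen the concern. It applies only once significance has been reached, so a trial shortened that way has already rejected the null and has lost no power. Its effect on type I error is a separate question.

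**Conclusion.** No change follows. The stated power is uncheckable from the protocol, not shown to be wrong. It holds if control two-year MACE is about 37% to 41% two-sided, or 31% to 34% one-sided, with 150 per arm, no loss and proportional hazards; a 10% loss raises the Schoenfeld figures to 41% and 34%. The protocol neither gives nor contradicts such a rate. The missing control rate, sidedness and loss allowance are assumptions that the sample-size section of an analysis plan can hold. Writing them down would alter neither the number of patients, the endpoint nor the analysis, and at the end of the trial the confidence interval for the hazard ratio will show what a null result can exclude, whatever power was planned.

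The conclusion would change if the analysis plan or the source study gave a control rate clearly below these thresholds. The stated 90% would then be too high, by the amounts in the table.

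### Section IV lets the sample size be cut once significance is reached, with no threshold beyond alpha .05, so the 5% error rate is not protected

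*Protocol*

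**What the plan says.** Section III defines the primary endpoint as a "composite of cardiac death, myocardial infarction (MI) or urgent (unplanned) coronary revascularisation (MACE) during 2 years follow up".

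Section IV takes 0.5 as the hazard ratio to be detected and sets an "estimated sample size up to 300 patients (up to 150 in each group), 90% power, alpha .05". The next sentence reads: "The patient sample size may be reduced if statistical significance been achieved". It gives no number or timing of looks, no adjusted threshold and no body to review comparative results, and it refers to no other document. The only independent committee the protocol describes adjudicates endpoints.

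Section VI states "There are no formal termination criteria for this study" and lets the sponsor end the study at any time. Section IX describes the randomisation as open label.

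**The concern.** Significance can be reached before the sample is complete only if the arms are compared while data accumulate. Each such comparison at an unadjusted .05 is a further chance of a false positive.

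The sentence also leaves open what happens after the threshold is crossed. There are two readings:

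- **Stop and report:** the crossing result becomes the trial's result.
- **Cut and follow:** enrolment stops, everyone already enrolled completes 2 years, and one test is then made at .05.

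The operating characteristics differ greatly, and Section VI does not settle which is meant. The rule acts on the only primary comparison. Once data have been looked at and enrolment cut on the strength of them, the error rate cannot reliably be restored. Under stop and report the effect estimate also suffers, because an early crossing needs an extreme observed hazard ratio.

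**Working it through.** **Inputs from the protocol (Section IV):** hazard ratio 0.5, power 90%, alpha .05, up to 150 patients per group. **Assumed:** a two-sided test, equally spaced looks, and the number of looks.

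**1. Events implied by the design.** The Schoenfeld formula gives d = 4(1.960 + 1.282)² / (ln 0.5)² = 87.5, so 88 events (72 if alpha is one-sided). The protocol gives no event rate, so its figure of 300 patients can be neither confirmed nor refuted. With 300 patients, 88 events means 88/300 = 29% of all patients, or a 2-year control risk of about 38%.

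**2. Type I error under stop and report.** One million null paths of the cumulative log-rank score were simulated, counting any look with |Z| > 1.96.

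| Looks | Either direction | False claim of benefit only |
|---|---|---|
| 1 | 5.0% | 2.5% |
| 2 | 8.3% | 4.2% |
| 3 | 10.7% | 5.4% |
| 5 | 14.2% | 7.1% |
| 10 | 19.3% | 9.6% |

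At one-sided .05 the rates are 8.0% (2 looks), 10.1% (3), 13.0% (5) and 17.1% (10), so the unstated sidedness does not change the conclusion.

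**3. Type I error under cut and follow.** This was a patient-level log-rank simulation with 300 patients, uniform accrual, the same 2-year risk in both arms, looks at equal event fractions, and 8,000 runs per setting (Monte Carlo standard error about 0.25 points). Entries are for 2 / 3 / 5 looks.

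| Accrual | Risk 20% | Risk 38% |
|---|---|---|
| 2 years | 5.1 / 5.9 / 5.5% | 4.5 / 5.5 / 5.3% |
| 4 years | 5.7 / 6.0 / 6.2% | 5.5 / 6.0 / 6.0% |
| 6 years | 5.9 / 6.3 / 7.2% | 6.0 / 6.5 / 6.7% |

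A separate 5-look run gave 5.1% to 6.6%, against 4.4% to 4.9% for a single test on the same simulated data.

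**4. Effect estimate under stop and report, planned for 88 events.** The log hazard ratio has information d/4, so crossing at d events needs an observed hazard ratio below exp(−1.96/√(d/4)). At 88 events this is exp(−1.96/√22) = 0.66. At the first of five looks (17.6 events) it is exp(−1.96/√4.4) = 0.39. Results for a first crossing in favour of the test arm with five looks:

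| True HR | Declared beneficial (before the last look) | Median reported HR | Single test: power | Single test: median HR if significant |
|---|---|---|---|---|
| 0.50 | 93% (87%) | 0.44 | 90% | 0.49 |
| 0.70 | 49% (41%) | 0.51 | 39% | 0.58 |
| 0.80 | 28% (23%) | 0.51 | 18% | 0.60 |

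With two looks the distortion is smaller: 91% (63% early) and a median of 0.47 at a true HR of 0.50, 43% (22%) and 0.53 to 0.54 at 0.70, and 22% (11%) and 0.54 at 0.80. A modest true effect would tend to be reported as close to the design value of 0.5.

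**5. A boundary that holds 5%.** Lan-DeMets O'Brien-Fleming-type spending was used, 0.025 per side, with one interim. With the interim at half the events, z = 2.963 then 1.969 (two-sided p of about .0031, then .0490). At 60% of events, z = 2.669 then 1.981 (.0076, then .0476). For HR 0.50 and 88 events:

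- **Single test:** drift = 0.693 × √22 = 3.251, so power = Φ(3.251 − 1.960) = 90.2%.
- **Interim at 50%:** power 90.1%. The chance of crossing at the interim is Φ(0.693 × √11 − 2.963) = 25%.
- **Interim at 60%:** power 89.9%. The chance of crossing at the interim is Φ(0.693 × √13.2 − 2.669) = 44%.

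**The case against.** The strongest reply is that boundaries, looks and reviewing bodies are commonly left to the SAP, which is not at hand. Significance is undefined in the sentence, alpha .05 could be an overall level kept by an adjusted boundary, and the wording is only permissive. This does not remove the point. What is at issue is a rule the protocol states, not a detail it omits. The sentence authorises a cut triggered by significance without pointing to any boundary or document, and a SAP with a proper boundary would still need this sentence brought into line.

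The second reply carries more weight. The text speaks of sample size, not of follow-up or the analysis date, and the endpoint is fixed at 2 years, so cut and follow is a natural reading. With 2-year accrual its inflation is small. Paired comparisons in a further simulation gave 5.2% against 5.2% for a single test, 5.1% against 4.6%, 4.5% against 4.4% and 6.1% against 5.7%. It is fair to conclude that clearly excess error depends on stop and report or on long accrual. The protocol excludes neither.

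Two qualifications stand. The two-sided rates include false findings of harm, so the benefit-only column is the relevant one if only benefit would trigger the cut. The effect-estimate and power figures also rest on 88 events. At a 20% control risk, 300 patients would give about 150 × (0.20 + 0.106) = 46 events and about 65% power, and a look at 44 events would then come near the end of the trial. Finally, the termination sentence in Section VI does not strictly contradict Section IV, but it supplies no limit either.

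**Conclusion.** The concern holds: the sentence is wrong as written and must be changed before any comparative look. Under stop and report, even one extra unadjusted look raises the two-sided error from 5% to 8.3%, and five looks raise it to about 14%. Under cut and follow, the error was about 4.5% to 7.2% in the settings examined, with little or no inflation when accrual is short. The size depends on the assumed number and spacing of looks, the accrual time and the event risk, none of which the protocol gives. Under stop and report the error always exceeds nominal, whatever the number of extra looks. Because the text permits either course, the level of a positive result could not be known.

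**What to change.** Choose one of two changes to Section IV.

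1. **No interim.** Delete the sentence, replace the open upper limit with a fixed number of patients or events, and state that the size will not be changed on comparative results. State also that the primary comparison is tested once, at two-sided .05, after all patients complete 2-year follow-up.
2. **A prespecified group-sequential rule.** For example, one interim at 44 of 88 primary events with a Lan-DeMets O'Brien-Fleming-type boundary (p of about .0031, then .0490), or at 60% of events (.0076, then .0476). Have people independent of the investigators review the comparative data. State whether enrolled patients complete 2 years after a crossing and which analysis is primary. If 88 events is not the planned total, set the look as a fraction of the total that is planned.

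Make the termination sentence in Section VI consistent with the choice.

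The cost is one or two sentences in an amendment and no extra patients. Given 88 events and HR 0.50, the interim costs at most 0.3 points of power (90.2% to 89.9%). What is lost is the freedom to cut enrolment at will: with these boundaries the chance of crossing at the interim is about 25% or 44% if the design effect is true.
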